5.6.1. Prior Treatment

Details of any medication or vaccines received prior to enrollment into the study will not be collected in the CRF.

5.6.2. Permitted Vaccines

Vaccinations, including Hib vaccination, may be given ≥ 4 days before or ≥ 7 days after study vaccination, except for BCG vaccine and oral vaccines, which are allowed at any time, according to local practice or national recommendations, at the discretion of the investigator.

5.6.3. Permitted Treatments

- A local anesthetic may be used at the site of the blood draw.
- Topical and inhaled corticosteroids may be used.
- Antipyretic medication may be used; however, prophylactic use should be discouraged.

Haemophilus influenzae Type b Vaccine:

- 13vPnC recipients in Cohort 1, 2, 3 or 4 will be offered Hib vaccinations according to local practice or national recommendations, at the discretion of the investigator. Refer to Section 5.6.2 for further details of when Hib vaccine may be given. Investigational sites will be reimbursed for any Hib vaccinations given. Hib vaccinations will be given outside of the study.
- Hib recipients in Cohort 2 will all be offered additional Hib vaccination(s) according to local practice or national recommendations, at the discretion of the investigator. Refer to Section 5.6.2 for further details of when Hib vaccine may be given. Investigational sites will be reimbursed for any Hib vaccinations given. Hib vaccinations will be given outside of the study.

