Prevenar 13, the 13-valent pneumococcal conjugate vaccine (13vPnC) was approved in China in October 2016 for the prevention of invasive pneumococcal disease in infants 6 weeks to 15 months of age. The approved regimen only allows vaccination with Prevenar 13 at 2, 4, 6 months for the primary series and the toddler or booster dose at 12 to 15 months of age. Prevenar, the 7-valent vaccine that was used as a comparator in the Phase 3 study in China had been approved through 5 years of age (up to the 6th birthday). The safety and immunogenicity of 7vPnC in children 7 months up to 5 years of age had been assessed in a post-licensure study (Study number B1841008).

The Center for Drug Evaluation (CDE) requested that safety and immunogenicity of Prevenar 13 be assessed in children 7 months to 5 years of age (before the 6th birthday). CDE also requested that Pfizer provide antibody persistence data through 5 years of age in children vaccinated as infants. This study is designed to support licensure of 13vPnC from

7 months through 5 years of age and to address both of these post licensure commitments from the CDE.

This study includes 4 separate cohorts broken down by age. Cohorts 2, 3 and 4 range in age from 7 months to 5 years of age (Cohort 2 - 7 months to <12 months of age; Cohort 3 - ≥ 1 year to <2 years; Cohort 4 - ≥ 2 years to <6 years of age). These three cohorts are of primary interest in obtaining licensure in the 7 months to 5 year age range and addressing the CDE request to obtain safety and immunogenicity data in this age group. Immune responses before and after the last vaccination in each of these age groups will be measured and used as a surrogate of efficacy. Cohort 1 will include infants 6 weeks to 2 months of age that will be vaccinated with 13vPnC according to the currently licensed infant schedule (2, 4, 6 and 12 to 15 months). Post vaccination serotype specific serum anticapsular IgG responses in Cohorts 2, 3, and 4 will be compared to the post infant series responses in Cohort 1 as a bridge to efficacy. Cohorts 2, 3, and 4 will also include a control group vaccinated with *Haemophilus influenzae* type b (Hib) vaccine. The Hib vaccinated infants and children will serve as controls for assessment of the safety and immunogenicity of Cohorts 2, 3, and 4.

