8.1.4. Time Period for Collecting AE/SAE Information

The time period for actively eliciting and collecting AEs and SAEs ("active collection period") for subjects in Cohort 1, begins from the time the subject's /parent(s)/legal guardian provides informed consent, which is obtained before the subject's participation in the study (ie, before undergoing any study-related procedure and/or receiving investigational product), through and including Visit 4 and from Visit 5 to Visit 6. Between Visits 4 and 5 and between Visits 6 and 7, only SAEs and newly diagnosed chronic medical conditions will be

recorded. The subject's parent/legal guardian will be asked to report any AEs that occur within 48 hours after the blood draw at Visits 8, 9, 10, and 11.

The time period for actively eliciting and collecting AEs and SAEs ("active collection period") for subjects in Cohort 2, 3, and 4, begins from the time the subject's /parent(s)/legal guardian provides informed consent, which is obtained before the subject's participation in the study (ie, before undergoing any study-related procedure and/or receiving investigational product) until 1 month after the last vaccination (13vPnC or Hib). At the 6-Month follow-up telephone contact (final telephone contact), the parent(s)/legal guardian will be contacted to inquire about SAEs, including hospitalizations and newly diagnosed chronic medical conditions since the previous visit.

For subjects who are screen failures, the active collection period ends when screen failure status is determined.

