5.2.1. Analyses for Binary Data

For immunogenicity results, the exact 2-sided 95% CIs (Clopper-Pearson CIs) will be provided for the proportions of subjects achieving an IgG concentration $\geq 0.35 \ \mu g/mL$, and the proportion of subjects with pneumococcal OPA titer \geq LLOQ for each vaccine group at defined sampling time point in each cohort, as defined in Section 3.2.1.

The exact CIs (Clopper-Pearson) for the various proportions of individual groups will be computed using the F distribution. If r is the number of responses and n is the number of subjects, then it follows that p=r/n is the estimate of the proportion of responses. An exact 95% CI can be computed by solving the following 2 equations. For the lower limit P_L ,

$$p_L = \frac{rF_L}{(rF_L + (n-r+1))}$$

and for the upper limit P_U ,

$$p_U = \frac{(r+1)F_U}{(n-r) + (r+1)F_U}$$

where F_L is the quantile from the F distribution for α =0.025, with numerator degrees of freedom equal to 2r and denominator degrees of freedom equal to 2(n–r+1). F_U is the quantile from the F distribution for α =0.975, with numerator degrees of freedom equal to 2(r+1) and denominator degrees of freedom equal to 2(n–r). When r equals 0, F_L should be set equal to 1.0 so P_L equals 0. When r equals n, F_U should be set equal to 1.0 so P_U equals 1.0.

The CI using the F distribution is described in Collett (1991) and implemented in SAS PROC FREQ.

The proportion differences for each serotype in 13vPnC between 1 month after the last vaccination of each cohort (Cohort 2, Cohort 3, Cohort 4) and 1 month after last vaccination of infant series of Cohort 1; and proportion differences between 13vPnC and Hib vaccine in Cohort 2, Cohort 3, Cohort 4 will be provided along with associated exact 2-sided 95% CIs by Chan and Zhang's method (1999).

Similarly, for the safety results in infants and children 7 months to <6 years of age (Cohorts 2, 3, and 4), the exact 2-sided 95% CIs will be provided by vaccine group in each Cohort for all primary safety endpoints, proportions of subjects reporting local reactions, systemic events, and AEs (including AEs occurring within the first 30 minutes after each vaccination).

For tier 1 AEs, an unconditional exact method for deriving the 95% CI for the risk difference and p-value proposed by Chan and Zhang (1999) will be used to compare 13vPnC with Hib vaccine.

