6.4.7. Nonstudy Vaccination and Nonstudy Medication

Nonstudy vaccination and nonstudy medication summaries will be provided with descriptive summaries. Each vaccine will be summarized according to the Anatomic Therapeutic Chemical (ATC) 4 classification system. The number and percentage of subjects receiving each vaccine will be tabulated for each vaccine group and total sample for each cohort. The denominator for the percentages is the number of subjects in the vaccine group or total sample in each cohort.

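### The tier 1 and tier 2 adverse event contrasts with Hib ignore the nonstudy Hib offered to the 13vPnC arm from day 7, and so can overstate 13vPnC risk

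*Protocol*

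**What the plan says.** **Role of the Hib arm.** Protocol 1.2 states: "The Hib vaccinated infants and children will serve as controls for assessment of the safety and immunogenicity of Cohorts 2, 3, and 4". Previous Hib vaccination is an exclusion (Protocol 4.2), so children enter Hib-naive.

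**The offer.** Protocol 5.6.3: "13vPnC recipients in Cohort 1, 2, 3 or 4 will be offered Hib vaccinations according to local practice or national recommendations". The sentence goes on to leave this to the investigator's discretion. Sites are reimbursed, and the doses count as given outside the study. The same section makes an offer of extra Hib to Cohort 2 Hib recipients, but none to Hib recipients in Cohorts 3 and 4.

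**Timing.** Protocol 5.6.2: "Vaccinations, including Hib vaccination, may be given ≥ 4 days before or ≥ 7 days after study vaccination".

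**Collection windows.** AEs are collected from consent to 1 month after the last study vaccination, and SAEs to 6 months (Protocol 2 and 8.1.4). Local reactions and systemic events are collected on Days 1 to 7 after each study dose (Protocol 7.2 and 7.3).

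**Analysis.** For tier 1 AEs, SAP 5.2.1 says that an exact method giving a risk difference, confidence interval and p-value "will be used to compare 13vPnC with Hib vaccine". Tier 2 events get a risk difference and interval. SAP 6.4.1 repeats both. The safety population is reported by study vaccine received (SAP 4.5).

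**Nonstudy vaccines.** Names and dates go on the CRF (Protocol 5.6, SAP 3.5.3.2). Their only planned use is in SAP 6.4.7: "Nonstudy vaccination and nonstudy medication summaries will be provided with descriptive summaries", as counts and percentages. The SAP does not relate these dates to AE onset by censoring, stratification or a sensitivity analysis.

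**The concern.** The comparator can be given to the test arm while that arm's AEs are still being counted. If a child randomised to 13vPnC takes up the offer on, say, day 10 and has an event caused by Hib, the tier tables place that event under 13vPnC. In Cohorts 3 and 4 the protocol makes no balancing offer to the control arm.

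What is at stake is the reading of the tier 1 and tier 2 contrasts. An excess in the 13vPnC arm could come from 13vPnC or from later Hib, and the planned output cannot separate the two. A true advantage of 13vPnC over Hib could be diluted in the same way. Cohort 4 shows the problem most clearly, because both arms receive one dose and share the same windows.

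**Working it through.** **1. Arm sizes.** The plan gives no size or power for the safety comparison, only the randomised numbers. With 150 evaluable and 15% nonevaluable, 150 / 0.85 = 176.5, so 177. At 2:1, 177 × 2/3 = 118 on 13vPnC and 59 on Hib. This matches Protocol 9.5 and Table 15.

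**2. Share of each window open to nonstudy Hib** (dose day = day 0, Hib permitted from day 7):

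- Cohort 4, AE window to Visit 2 at day 28 to 42: (28 − 7)/28 = 21/28 = 75%; (42 − 7)/42 = 35/42 = 83%.
- Cohort 3, 13vPnC arm at minimum spacing (56 days, then 28): between doses 56 − 4 − 7 = 45 days; after dose 2, 28 − 7 = 21 days; (45 + 21)/84 = 66/84 = 79%.
- SAE follow-up at 168 to 196 days: 161/168 = 96% to 189/196 = 96%.

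These are permitted days, not exposure.

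**3. Possible size, by assumption only.** The documents give neither uptake nor any Hib AE risk. Suppose both vaccines carry the same risk h of an event, a fraction u of the 13vPnC arm takes Hib early enough for its whole risk to fall in the window, and the two risks act independently. The 13vPnC arm's risk is 1 − (1 − h)(1 − uh), so the spurious excess is uh(1 − h). The bracketed figure is the approximate chance of a nominally significant excess at 118:59 (normal approximation; 2.5% when u = 0).

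| h | u = 25% | u = 50% | u = 100% |
|---|---|---|---|
| 5% | 1.2 points (4.5%) | 2.4 points (7.4%) | 4.8 points (16.7%) |
| 10% | 2.3 points (5.9%) | 4.5 points (11.8%) | 9.0 points (32.2%) |
| 20% | 4.0 points (8.2%) | 8.0 points (20.0%) | 16.0 points (59.2%) |

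The 5% row sits at the tier 2 threshold for a preferred term (SAP 3.4.1). The 20% row is nearer to any-AE incidence, for which the SAP plans no between-arm test.

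**4. Dilution of a true advantage.** Take 13vPnC 10% and Hib 20%, a true difference of −10 points. At u = 50% the 13vPnC arm shows 1 − 0.9 × 0.9 = 19%, a difference of −1 point. At u = 100% it shows 1 − 0.9 × 0.8 = 28%, a difference of +8 points.

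**5. Why censoring must treat both arms alike and allow for time since dose.** Assume no Hib effect, with an AE rate of 0.02 per day for 7 days and then 0.005 per day to day 28.

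- Uncensored: (7 × 0.02 + 21 × 0.005)/28 = 0.245/28 = 0.00875 per day.
- Half the arm censored at day 14: (0.245 + 0.175)/(28 + 14) = 0.42/42 = 0.010 per day.
- All censored at day 7: 0.14/7 = 0.020 per day, or 2.3 times the uncensored rate.

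Crude censoring of the 13vPnC arm alone would thus create the false excess it is meant to remove.

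**The case against.** A reader might infer that the whole randomised safety comparison becomes 13vPnC plus Hib against Hib. The documents do not support that, for three reasons that stand.

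- Hib is offered at the investigator's discretion and uptake is not stated. Only children who accept inside the window are doubly exposed.
- In Cohort 2 both arms are offered nonstudy Hib, so the offer there is not one-way.
- The 7-day rule largely protects Day 1 to 7 reactogenicity, itself a primary safety endpoint. What remains is Hib given 4 or more days before a later study dose. Only Cohort 2 dose 2 then has a control diary for comparison, since controls receive nothing at Cohort 2 Visit 3 or Cohort 3 Visit 2. Local reactions are recorded at the study injection site, so only systemic events and antipyretic use could carry over.

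It can also be said that the primary safety objective is worded as incidence rates, that SAP 5.1 calls the study descriptive, that SAP 6.4.1 cautions against causal reading, and that investigators assess causality for every AE. This lowers the importance but does not remove the point. The protocol names Hib as the safety control, and the tier contrasts and p-values are planned. They are not described as limited to events judged related.

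Lastly, the likely bias runs against 13vPnC, so it is more likely to raise a false signal than to hide a real one. That is fair. An observed excess would still be hard to attribute.

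**Conclusion.** The concern holds in a limited form. The planned tier 1 and tier 2 risk differences and the tier 1 p-values can mix 13vPnC with 13vPnC plus Hib, and so can overstate 13vPnC risk relative to Hib. It applies most clearly to Cohorts 3 and 4 and less to Cohort 2.

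The only size that rests on the documents is the overlap: 75% to 83% of the Cohort 4 AE window is open to nonstudy Hib. The excess in percentage points is unknown. The table above is a range under assumed uptake and risk, and should not be read as an estimate. Nor do the any-AE-sized figures carry over to single preferred terms, which is where the tier 2 contrasts are made. The tier 1 list is held in a separate safety review plan and SAP 3.4.1 is partly redacted, so the affected events cannot be named.

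**What to change.** Keep the planned tables and add the following to SAP 5.2.1 and 6.4.1.

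- **(a) Sensitivity analysis.** Tier 1 and tier 2 risk differences for AEs with onset from the day of dose 1 to day 6. Use the recorded dates to confirm that no nonstudy injectable vaccine fell in that interval, because Protocol 5.3.3 also refers to permitted concomitant vaccines. Dose 1 is the clean choice since entrants are Hib-naive.
- **(b) Supportive rate comparison.** AE rates stratified by or adjusted for time since study dose, with follow-up censored at the first nonstudy Hib dose in both arms. In Cohorts 3 and 4 most censoring would be expected in the 13vPnC arm, so the adjustment is essential. It assumes that, given time since dose, taking up Hib is unrelated to AE risk.
- **Reporting.** Nonstudy Hib uptake and timing by arm and cohort. Interpret any tier 1 or tier 2 difference from Hib alongside (a) and (b).

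The cost is SAP wording and extra tables from data already collected, with no change to study conduct. Analysis (a) has a shorter window and fewer events. SAP Section 2 says the primary report analyses are already done, so these additions should be labelled supplemental. They could go in the supplemental report that repeats the analyses with the additional 280 subjects.

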5.6.4. Mandatory Concomitant Vaccines

None

5.6.5. Prohibited Vaccines and Medications

No pneumococcal vaccines (licensed or investigational) other than those described in this study may be given prior to or during the study.

Local anesthetic cream should not be used at the site of investigational product administration.

Prophylactic use of antipyretic and other pain medications to prevent symptoms that might occur as a result of investigational product administration should be discouraged; however, it is recognized that use of antipyretic medication is a matter of parental choice and local clinical practice.

6. STUDY PROCEDURES

Before enrollment and before any study-related procedures are performed, voluntary written study-specific informed consent must be obtained from the parent/legal guardian of the subject. Each signature on the informed consent document (ICD) must be personally dated by the signatory. A copy of the signed and dated ICD must be given to the parent/legal guardian. The source data must reflect that the informed consent was obtained before participation in the study.

Procedures considered to be part of standard routine care (eg, physical examination) may be performed before the ICD is signed but, for the purposes of the study, must be done on the day of first vaccination.

6.1. Cohort 1

6.1.1. Cohort 1: Visit 1, Vaccination 1 (42 to 56 Days of Age)

- Obtained informed consent from the subject's parent(s)/legal guardian(s) prior to performing any protocol-required procedures.
- Assign a subject number using the IRT or equivalent system.
- Obtain and record the subject demography (including full date of birth, sex and race. The date of birth will be collected to critically evaluate the immune response and safety profile by age).
- Obtain and record the subject's medical history.
- Record any nonstudy vaccinations. Note: vaccinations may be given ≥4 days before or ≥ 7 days after study vaccination, except for BCG vaccine and oral vaccines, which are allowed at any time, according to local practice or national recommendations, at the discretion of the investigator.
- Perform a physical examination evaluating any clinically significant abnormalities in the following: general appearance, skin, head, eyes, ears, nose, throat, heart, lungs, abdomen, extremities, back/spine, neurological status, and lymph nodes including worsening of medical history conditions. Results must be recorded on source documents and the Medical History or AE page of the CRF as appropriate.
- Measure and record the subject's axillary temperature.

- Ensure that all inclusion criteria and none of the exclusion or temporary delay criteria are met.
- Collect a blood sample (approximately 5 mL). Blood must be drawn from peripheral veins (eg, arm, foot, or scalp veins). Drawing blood from central veins (eg, jugular or femoral veins), which may increase the risk associated with study participation, is not permitted.
- Administer a single 0.5-mL intramuscular injection of 13vPnC into the subject's left limb (left anterolateral thigh muscle or deltoid of the left arm) in accordance with the local package insert.
- Observe the subject for at least 30 minutes after vaccination for any significant acute reactions. Any AE noted during the observation period should be recorded in the source documents and in the AE section of the CRF.
- Ask the caregiver to contact the investigator or other site staff immediately if any significant illness or hospitalization occurs during the study period.
- Schedule an appointment with the caregiver for the next study visit.
- The investigator or an authorized designee completes the CRF and updates the investigational product accountability records.

6.1.2. Cohort 1: Visit 2, Vaccination 2 (42 to 70 Days After Visit 1)

- Based on clinical evaluation, determine whether any AEs (including SAEs) have occurred since the last study visit and record them on the CRF.
- Record any nonstudy vaccinations.
- On the day of vaccination, measure and record the subject's axillary temperature.
- Ensure that the subject continues to be eligible for the study; refer to Subject Withdrawal section of the protocol.
- Ensure the subject does not meet any of the temporary delay criteria.
- Administer a single 0.5-mL intramuscular injection of 13vPnC into the subject's left limb (left anterolateral thigh muscle or deltoid of the left arm) in accordance with the local package insert.
- Observe the subject for at least 30 minutes after vaccination for any significant acute reactions. Any AE noted during the observation period should be recorded in the source documents and in the AE section of the CRF.

- Ask the caregiver to contact the investigator or other site staff immediately if any significant illness or hospitalization occurs during the study period.
- Schedule an appointment with the caregiver for the next study visit.
- The investigator or an authorized designee completes the CRF and updates the investigational product accountability records.

6.1.3. Cohort 1: Visit 3, Vaccination 3 (42 to 70 Days After Visit 2)

- Based on clinical evaluation, determine whether any AEs (including SAEs) have occurred since the last study visit and record them on the CRF.
- Record any nonstudy vaccinations.
- On the day of vaccination, measure and record the subject's axillary temperature.
- Ensure that the subject continues to be eligible for the study; refer to Subject Withdrawal section of the protocol.
- Ensure the subject does not meet any of the temporary delay criteria.
- Administer a single 0.5-mL intramuscular injection of 13vPnC into the subject's left limb (left anterolateral thigh muscle or deltoid of the left arm) in accordance with the local package insert.
- Observe the subject for at least 30 minutes after vaccination for any significant acute reactions. Any AE noted during the observation period should be recorded in the source documents and in the AE section of the CRF.
- Ask the caregiver to contact the investigator or other site staff immediately if any significant illness or hospitalization occurs during the study period.
- Schedule an appointment with the caregiver for the next study visit.
- The investigator or an authorized designee completes the CRF and updates the investigational product accountability records.

6.1.4. Cohort 1: Visit 4, Post-Infant Dose Follow-up (28 to 42 Days After Visit 3)

- Based on clinical evaluation, determine whether any AEs (including SAEs) have occurred since the last study visit and record them on the CRF.
- Record any nonstudy vaccinations.
- Ensure that the subject continues to be eligible for the study; refer to Subject Withdrawal section of the protocol.

- Collect a blood sample (approximately 5 mL). Blood must be drawn from peripheral veins (eg, arm, foot, or scalp veins). Drawing blood from central veins (eg, jugular or femoral veins), which may increase the risk associated with study participation, is not permitted.
- Schedule an appointment with the caregiver for the next study visit.
- The investigator or an authorized designee completes the CRF and updates the investigational product accountability records.

